5.4.9 Discontinuation of study treatment

Patients may voluntarily discontinue study treatment for any reason at any time. In the case that the patients would want to discontinue the treatment, it is particularly important to ask if they would be willing to remain in the trial and share his/her safety and vital status information until the scheduled final visit in order to ensure the scientific integrity of the trial.

The investigator should discontinue study treatment for a given patient and/or withdraw the patient from the study if, on balance, he/she believes that continuation would be detrimental to the patient's well-being.

Study treatment *must* be discontinued under the following circumstances:

- Patients who experience 5 or more asthma exacerbations during the treatment epoch that required treatment with systemic corticosteroids.
- Adolescent patients (12 to 17 years old) who experience one asthma exacerbation requiring hospitalization
- Patients with > 50% decrease in FEV₁ from baseline (e.g Visit 101) confirmed by a repeat measurement the same day during the run-in or during the treatment epoch (baseline being then Visit 201).
- If a patient develops a medical condition/AE that requires prolonged use of prohibited treatment as per [Section 5.4.8](#) or if patient exhibits a behavior of non-compliance regarding prohibited medications.

Any other protocol deviation that results in a significant risk to the patient's safety

Discontinuation of study treatment (but continued study participation)

- For this study it is very important to continue collecting data, especially vital status, on all patients whether or not he/she completes treatment to continue collecting safety information. The patient should NOT be considered withdrawn from the study due to study treatment interruption or discontinuation.
- If premature discontinuation of study treatment occurs, the patient should return to the clinic as soon as possible for a study treatment discontinuation visit. The investigator must determine the primary reason for the patient's premature discontinuation of study treatment and record this information on the End of Study Treatment e-CRF page. The investigator and study staff must discuss with the patient the continued participation in the study by maintaining regular telephone contact with him/her or with a person pre-designated. This telephone contact should preferably be done according to the study visit schedule.

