6.4.5 Asthma Exacerbation

All type of asthma exacerbations meeting below criteria must be recorded in the Asthma Exacerbation Episode CRF (Asthma worsening as defined above should also be reported).

A **severe asthma** exacerbation (Draft note for guidance on clinical investigation of medicinal products for treatment of asthma CHMP/EWP/2922/01 Rev.1) is defined as an aggravation of asthma symptoms (like shortness of breath, cough, wheezing, or chest tightness) that requires systemic corticosteroids (SCS) for at least three consecutive days and/or a need for an ER visit, hospitalization due to asthma or death due to asthma.

- Start date and end date:

- In case of the use of SCSs for at least three days, the first day of treatment will determine the onset date of the event while the last day of treatment will define the stop date.

In the event that an ER visit and/or hospitalization due to asthma exacerbation were not associated with a course of SCSs as described above, start and end dates would be defined by the corresponding dates entered by the Investigator in the CRF.

A **moderate asthma** exacerbation in this protocol is defined as the occurrence of two or more of the following:

1. Progressive increase of at least one of the asthma symptoms like shortness of breath, cough, wheezing, or chest tightness. The symptoms should be outside the patient's usual range of day-to-day asthma and should last at least two consecutive days.
2. Increased use of "rescue" inhaled bronchodilators defined by:
 - > 50% increase in SABA use and > 8 puffs on 2 out of any 3 consecutive days compared to baseline captured

Or

- Night time awakenings requiring SABA use on at least 2 out of any 3 consecutive nights

3. Deterioration in lung function, which last for two days or more but usually not severe enough to warrant SCSs for more than 2 days or hospitalization. This deterioration would be defined by:

> 20% decrease in FEV₁ from baseline value

Or

≥ 20% decrease in am or pm PEF from baseline on 2 out of any 3 consecutive days compared to baseline.

Or

< 60% of PEF compared to baseline

- A **mild** asthma exacerbation is defined as the occurrence of one of the following criteria:

1. Deterioration of at least one asthma symptoms like shortness of breath, cough, wheezing or chest tightness.

2. Increased use of "rescue" inhaled bronchodilators

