3. Deterioration in lung function, which last for two days or more but usually not severe enough to warrant SCSs or hospitalization.

This deterioration would be defined by:

> 20% decrease in FEV₁ from baseline value

Or

≥ 20% decrease in am or pm PEF from baseline on 2 out of any 3 consecutive days compared to baseline.

Or

< 60% of PEF compared to baseline

“Start and end dates” of each reported event in the CRF will be used to determine whether two consecutively reported events should be considered as separate events or as a prolonged.

If a second exacerbation is reported less than 7 days after the end date of a previous episode, then this will be assumed to be one continuous exacerbation with the start date taken from the first episode and the end date from the second or last episode. If two events are merged based on this “7 day rule”, the highest reported severity will be used to describe the overall severity of the prolonged event.

The treatment of asthma exacerbations including the initiation of systemic corticosteroids should be done according to investigator’s or treating physician’s medical judgement and should be in line with national and international recommendations. If systemic corticosteroids are required, a patient may return to the study after successfully completing a taper of approximately 7-10 days. If patients require significantly longer treatment periods or chronic administration, they must be discontinued from treatment.

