9.1 Analysis sets

The following analysis sets are defined for data analysis.

The randomized (RAN) set will consist of all patients who were assigned a randomization number, regardless of whether or not they actually received study medication.

The Full Analysis Set (FAS) will consist of all patients in the RAN set who received at least one dose of study medication. Following the intent-to-treat principle, patients will be analyzed according to the treatment they were assigned to at randomization.

The Per-Protocol set (PPS) will include all patients in the FAS who did not have any major protocol deviations. Major protocol deviations will be defined in the statistical analysis plan prior to database lock and the un-blinding of the study. Patients will be analyzed according to the treatment they received.

The Safety Set will consist of all patients who received at least one dose of study medication. Patients will be analyzed according to the treatment they received. [REDACTED]

The FAS will be used in the analysis of all efficacy variables. The RAN set will be used for a summary of patient disposition, demographics and baseline characteristics. The PPS will be used for supportive analysis of the primary analysis only. The Safety Set will be used in the analysis of all safety variables.

Note that the FAS and Safety Sets are the same except that the Safety Set allows the inclusion of non-randomized patients who received study drug in error. Also, the FAS assign randomized treatment and the Safety Set assigned received treatment.

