2.2 Analysis sets

The following analysis sets are defined:

- The randomized (RAN) set will consist of all patients who were assigned a randomization number, regardless of whether or not they actually received study medication. Patients in RAN will be analyzed according to the treatment they were randomized to. The RAN set will be used for a summary of patient disposition, demographics and baseline characteristics.
- The Full Analysis Set (FAS) will consist of all patients in the RAN set who received at least one dose of study medication. Following the intent-to-treat principle, patients will be analyzed according to the treatment they were assigned to at randomization. The FAS will be used in the analysis of all efficacy variables.
- The Per-Protocol set (PPS) will include all patients in the FAS who did not have any major protocol deviations. Major protocol deviations will be defined in the validation analysis plan prior to database lock and the un-blinding of the study. The list of major protocol deviations is available in [Appendix 16.1.9](#). Patients will be analyzed according to the treatment they received. The PPS will be used for supportive analysis of the primary analysis only.
- The Safety Set will consist of all patients who received at least one dose of study medication including non-randomized patients who received study drug in error. Patients will be analyzed according to the treatment they received. If patients switch double-blind treatment during the study, they will be counted and analyzed only once according to their initial treatment. The safety set will be used in the analysis of all safety variables.

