16.1.9.2 Major protocol deviations and other exclusion criteria

The following protocol deviations will be considered as major and will lead to exclusion of patients from analysis sets:

Exclusions from per-protocol set:

- INCL01: Age < 12 years or > 75 years or missing
- INCL03: No current diagnosis of persistent Asthma of at least 12 months prior to V1
- INCL04.A4: Patient not treated with medium/high dose ICS or LOW dose ICS/LABA combination for at least 3 months and/or not at stable dose 30 days prior to Visit 1
- INCL05: ACQ score < 1.5 at V101 and/or V102
- INCL05.01: ACQ INVALID ASSESSMENT; Patient used invalidated ACQ7 at Visit 101 and/or Visit 102.
- INCL06.A4: Pre- Bronchodilator FEV1 at V101 and V102 < 50% or \geq 85% of predicted normal at visit 101
- INCL06.01: Patient has not achieved assessments according to ATS/ERS criteria
- INCL07: Patient has not achieved an acceptable spirometry result and does not have historical reversibility or bronchoprovocation
- INCL07.01: Patient has not achieved an acceptable spirometry result and does not have Historical reversibility or bronchoprovocation according to ATS/ERS as per source documentation
- EXCL01: Patient has a smoking history of > 10 pack years or missing
- EXCL01.01: Patient smoked or inhaled tobacco within the 6 month period prior to V1
- EXCL01.02: Patients smoking nicotine inhaler at inclusion.
- EXCL02: Asthma attack/exacerbation requiring SCS or hospitalization or ER visits within 6 weeks prior to V1
- EXCL03: History of severe asthma exacerbation requiring intubation prior to visit 1
- EXCL05: Asthma exacerbation within 4 weeks prior to V1
- EXCL05.01: Respiratory Tract Infection or asthma worsening between screening and run-in 102 visits
- EXCL05.02: Respiratory Tract Infection within 4 weeks prior to V1
- EXCL06: Visual clinical significant oropharyngeal candidiasis between visit 1 and visit 102
- EXCL07: Chronic condition affecting upper respiratory tract
- EXCL08: Patient has a history of chronic lung diseases other than asthma

- EXCL11: Investigational drugs used within 5 half lives or until the return of baseline pharmacodynamic effect whichever is longer
- EXCL24: Patient is not on maintenance immunotherapy for allergies for at least 3 months prior to V101
- EXCL27: Unable to use dry powder inhaler device at V101 and/or V201
- EXCL28: Patient has history of alcohol or other substance abuse
- EXCL33.A4: Use of LAMA within 3 months prior to Visit 101

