- OTH08: Patient not having correct run in medication (i.e. 100mcg accuhaler or 125 mcg via MDI inhaler) or dose equivalent
- COMD07: Use of parenteral or oral corticosteroids less than 4 weeks prior to visit 101
- COMD08: Intra muscular corticosteroid less than 3 months prior to Visit 101
- COMD09: Use of Ige inhibitor less than 4 months prior to visit 101
- COMD10: Xanthine's use less than 7 days prior to visit 101
- COMD12: Last LABA washout more than 4 days prior to visit 101 or last ICS wash out more than 7 days before visit 101
- OTH06: Compliance failure of the patient influencing the safety and efficacy data as per investigator judgement
- OTH04: Patient receiving investigational drug other than study drug during the course of the study
- COMD05: Leukotriene antagonists and leukotriene synthesis inhibitors taken less than 7 days prior to visit 101
- COMD06: Use of SABA other than rescue medication, not discontinued at Visit 1
- COMD11: LABA taken less than 48h before Visit 101
- COMD01: Banned asthma related Concomitant medication
- WITH01: More than 5 exacerbation and still on treatment
- WITH02: Adolescent patient experience one severe exacerbation requiring hospitalization (ER>24) and is still on treatment

Exclusions from full analysis set and per-protocol set:

- OTH05: Patient Randomized more than one Trial.
- OTH14: Patient randomized more than once into this trial

Exclusions from full analysis set, per-protocol set, safety set, [REDACTED]:

- OTH02: Patient randomized but did not receive study drug

Exclusions from randomized set, full analysis set, per-protocol set, [REDACTED]:

- Patient received study drug but was not randomized

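### The per-protocol exclusion code WITH01 starts one exacerbation later than the protocol's mandatory stopping rule

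*SAP*

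**What the plan says.** Protocol 5.4.9 lists situations in which study treatment must "be discontinued under the following circumstances". The first is "Patients who experience 5 or more asthma exacerbations during the treatment epoch that required treatment with systemic corticosteroids". The second concerns adolescents with one exacerbation that leads to hospitalisation.

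Protocol 9.1 leaves the content of the PPS to the SAP: "Major protocol deviations will be defined in the statistical analysis plan prior to database lock and the un-blinding of the study". SAP 16.1.9.2 supplies the list, introduced by "The following protocol deviations will be considered as major and will lead to exclusion of patients from analysis sets". Among the PPS exclusions is "WITH01: More than 5 exacerbation and still on treatment". The next code, WITH02, covers an adolescent who stays on treatment after an exacerbation needing hospitalisation.

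On the role of the set, SAP 2.2 states: "The PPS will be used for supportive analysis of the primary analysis only".

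**The concern.** WITH01 looks like the deviation code for breaking the first stopping rule in protocol 5.4.9. WITH02 mirrors the second rule, and no other protocol rule stops treatment at a count of exacerbations. Yet the two texts put the cut at different places. Five events satisfy the protocol's condition but not the SAP's.

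SAP 2.6.1.4 describes the PPS analysis as showing the effect in patients who adhered to the protocol. A patient who met a mandatory stopping rule and was kept on the drug is not such a patient, but the code leaves that patient in. What is at stake is the correct make-up of this one supportive set.

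**Working it through.** **Comparing the two rules.** The plan has no figure of its own to reproduce, so the first step is a logical check. For a patient still on treatment, let T be the number of all exacerbations and S the number treated with systemic corticosteroids (S ≤ T).

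- Protocol 5.4.9 is breached when S ≥ 5.
- WITH01 read word for word applies when T > 5.
- WITH01 read as shorthand, with the steroid condition implied, applies when S > 5.

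| Patient still on treatment | Protocol 5.4.9 | WITH01, word for word | WITH01, steroid condition implied |
|---|---|---|---|
| T = 5, S = 5 | breach | not excluded | not excluded |
| T ≥ 6, S = 5 | breach | excluded | not excluded |
| S ≥ 6 | breach | excluded | excluded |
| T ≥ 6, S ≤ 4 | no breach | excluded | not excluded |
| T ≤ 5, S ≤ 4 | no breach | not excluded | not excluded |

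The first row is wrong on both readings. That is the point that does not depend on how the label is interpreted. The condition that the patient is still on treatment does not repair it, because treatment should already have stopped at the fifth event.

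**Is it caught or explained elsewhere?** OTH06 concerns a failure of compliance by the patient, as judged by the investigator; here the site failed to stop treatment. COMD01 concerns banned asthma medication, but protocol 5.4.8 permits systemic corticosteroids for exacerbations. SAP 2.1.5, which records changes to the planned analyses, does not mention a new threshold.

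**How many patients?** The documents give no rate of steroid-treated exacerbations, so these inputs are assumptions: rate m = 0.1 to 0.5 per patient-year and negative binomial dispersion k = 1 to 3. The 2000 patients come from protocol 9.8. The PPS analysis supports the Week 26 endpoint, so take half a year: μ = 0.5m.

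With r = 1/k and p = r/(r + μ), the chance of exactly five events is

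P(5) = [r(r+1)(r+2)(r+3)(r+4)/120] × p^r × (1 − p)^5.

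- Lowest case, m = 0.1, k = 1: μ = 0.05 and P(5) = 0.05^5/1.05^6 = 2.33 × 10⁻⁷. Times 2000, this is 0.0005 patients.
- Highest case, m = 0.5, k = 3: μ = 0.25, r = 1/3, p = 0.571. P(5) = 0.1248 × 0.830 × 0.01446 = 0.00150. Times 2000, this is 3.0 patients.
- With rates up to 0.3 the maximum (k = 3) is 0.64 patients.
- In the four arms of the primary contrasts (1600 patients), the two maxima become 3.0 × 0.8 = 2.4 and 0.64 × 0.8 = 0.51.

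All of these are ceilings, because they assume that nobody stops treatment at the fifth event. Only patients who were wrongly kept on treatment are misplaced.

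**The case against.** The strongest defence is that protocol 9.1 lets the SAP decide which deviations are major and does not require the list to copy 5.4.9. It does not copy it in full: 5.4.9 also requires stopping after a confirmed fall in FEV₁ of more than 50%, and no WITH code covers that. The SAP could have meant only the clearer breach, a sixth event on treatment, to count. That is possible, so intent is not proven. But the SAP gives no reason for six, and WITH02 follows the neighbouring stopping rule. A slip is the more natural explanation.

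A second defence is that the entries are loose labels. EXCL24, read word for word, excludes patients who are not on immunotherapy, which reverses the protocol's criterion. SAP 2.2 also refers to a validation analysis plan that is not among the documents, although it points to this appendix for the list. This defence has force against one tempting inference: that WITH01 also throws out compliant patients with, say, six mild exacerbations. That follows only from the word-for-word reading, and in a list of loose labels the documents do not support relying on it. Shorthand does not, however, turn five or more into more than five.

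A reader might also infer a larger effect from two calculations.

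- Over a full year, the same assumptions give 0.01 to 14.3 of 2000 patients with exactly five events. But a breach after Day 184 comes after the Week 26 measurement that the PPS analysis is there to support.
- Five separate events could in principle end by Day 39, using three-day courses ("that requires systemic corticosteroids (SCS) for at least three consecutive days") and the merging rule ("If a second exacerbation is reported less than 7 days after the end date of a previous episode"). This is a best-case minimum. With the 7 to 10 day taper in protocol 6.4.5 it becomes Day 59 to 74. It shows only that a breach before Day 184 is possible.

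Finally, SAP 2.6.1.1.1 sets FEV₁ values within 7 days of systemic corticosteroids to missing, so some of these patients may contribute no Week 26 value at all.

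**Conclusion.** WITH01 is wrong as written, and the matter is minor. The threshold mismatch stands on the text of the two documents and needs no assumption beyond WITH01 being the code for the 5.4.9 exacerbation rule. The missing steroid and treatment-epoch qualifiers may be shorthand and are worth tidying, but they carry no weight on their own.

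The size rests entirely on the assumed rates: at most about 3 of 2000 patients by Week 26, in most of the scenarios fewer than one, and fewer still once those who stopped as required are removed.

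A reader might infer that the trial's main result is exposed. It is not: the primary analysis uses the FAS, which WITH01 does not touch. Nor does the code change the stopping rule that investigators follow. The documents give no basis for stating a direction or size of bias in the PPS estimate.

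**What to change.** Reword WITH01 to: *5 or more asthma exacerbations requiring systemic corticosteroids during the treatment epoch and still on treatment*. If a threshold of six was intended, say so and give the reason.

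The cost is one line in the SAP deviation list, with no new data. SAP Amendment 2 already corrected a deviation identifier in this section. The change belongs before the unblinding for the Week 26 analysis, so that PPS membership does not depend on a later interpretation. The programmed deviation flag should be checked against the new wording at the same time.

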16.1.9.3 Assessment windows, baseline and post-baseline definitions, missing data handling

16.1.9.3.1 Data pooling and assessment windows

Data from unplanned or unscheduled visits or the early treatment/study discontinuation visits will be listed. For patients who do not complete the study, the treatment discontinuation visit will be an unscheduled visit.

Clinical laboratory measurements, vital signs and ECG data from unplanned or unscheduled visits will only be included in the summaries of the notable values and extreme values. All efficacy data (including spirometry data) from these visits will not be used for missing data imputation unless specified otherwise.

Laboratory, vital signs, and ECG values that have complete data and time values will be slotted into pre- or post-dose assessment based on the actual date/time. For values with missing date/time, scheduled visit date and time will be used. This rule will be applied to data from scheduled visits only. If a measurement scheduled as pre-dose is actually performed post-dose, or vice versa, the data will not be used for by time point assessments.

16.1.9.3.2 Baseline measurements

In general, baseline is defined as the last measurement before the first dose of study drug at Day 1.

1) For all **FEV₁, FVC, and FEF₂₅₋₇₅** endpoints, the baseline value is defined as the average of the values taken at -45 and -15 min prior to first dose of study drug at the evening of Day 1. Checks will be performed to ensure both values were indeed taken prior to the first dose of study drug. If one of the -45 and -15 min values is missing (or is not confirmed to be pre-dose) then the remaining non-missing value will be taken as the baseline. If both values are missing (or not confirmed to be pre-dose), then the last out of the pre-bronchodilator measurements taken at the run-in Visits 101 and 102 or at unscheduled run-in visits will be used as the baseline. If the FEV₁, FVC or FEF₂₅₋₇₅ measurements are missing both on Day 1 and at run-in visits, the respective baseline values will be set to missing. Measurements taken within 6 hours of rescue use, and/or within 7 days of systemic corticosteroid use, and/or 3 months of single depot corticosteroid injection, will be set to missing.

For all baseline spirometry measurements, we exclude the implausible values. Specifically, if a patient has implausible FEV₁ value (defined as > 7 L) at baseline assessment, all spirometry measurements related to that assessment will be excluded.

2) For the **ACQ** scores, the baseline value is defined as the score obtained at Day 1 (V102). If the value is missing, the last measurements from run-in visit 101 or unscheduled run-in visits will be used.

3) For patient **diary data (PEF, symptoms, and rescue medication use)**, the baseline values are defined as the average from all non-missing records taken in the run-in period over 14 days from Visit 101 up to one day before first dose of study drug (i.e., from Day -14 to Day -1 inclusively). Missing diary data will not be imputed.

Baseline PEF will be calculated separately for morning and evening values.

The night-time symptom score consists of one question 'How did you sleep last night?' which has to be answered with scores from 0 = 'I did not wake up because of any breathing problems.' up to 4 = 'I had difficulty sleeping because of my breathing problems even though I used my rescue medication.' The morning score consists of the question 'Did you have asthma symptoms upon awakening in the morning?' which has to be answered with scores from 0 = 'None' up to 4 = 'Very Severe'. There are 5 questions including the today's severity of shortness of breath, wheeze, cough, and chest tightness during the past 12 hours, and 'Did your respiratory symptoms stop you from performing your usual daily activities?' which are part of the daytime symptom score. All have to be answered with a score from 0 = 'None / Not at all' up to 4 = 'Very Severe / Completely'. The average of the 5 scores is defined as the daytime symptom score. The baseline scores will be derived by averaging over the days of the run-in period with non-missing data, separately for each score, the night-time, morning, and daytime symptom score.

The baseline total daily symptom score will be obtained in the first step by adding the night-time symptom score, the morning score, and the mean daytime symptom score for each single day. In the second step, these daily symptom scores will be averaged over the days of the run-in period with non-missing data. The score is in the range from 0 to 12. For the derivation of the total daily symptom score, all 3 scores have to be available at that day. Otherwise a total daily symptom score will not be calculated for that day.

Rescue medication use will be analyzed separately for the number of puffs during daytime, night-time, and over the complete 24 hours. Baseline is defined as the average number of puffs per day in the run-in period. If for the value over the whole day (24 hours) the number of puffs is missing for part of the day (either day-time or night-time) then a half day will be used in the denominator to calculate the average value. Any values > 30 for the number of puffs of rescue medication in a 12 hour period will be set to missing. These high numbers are not realistic and could impact the analyses.

If a patient has less than 7 days with non-missing data, then the respective baseline value will be set to missing.

4) **Laboratory data** include hematology, biochemistry, urinalysis, and plasma cortisol. Baseline laboratory data is defined as the assessment taken 20 minutes pre-dose at Day 1. Checks will be performed to ensure the assessments were indeed taken prior to the first dose of study drug on Day 1. If this assessment is missing or not confirmed to be pre-dose, the last value taken at the run-in Visit 101 or at an unscheduled visit before the first administration of study drug will be used for baseline. Otherwise, the baseline laboratory data will be set to missing.

5) **Vital signs** include pulse rate and systolic and diastolic blood pressures. Baseline vital signs are defined as the assessment taken 25 minutes pre-dose at Day 1. Checks will be performed to ensure the assessments were indeed taken prior to the first dose of study drug on Day 1. If this assessment is missing or not confirmed to be pre-dose, the last value taken at the run-in Visit 101 or at an unscheduled visit before the first administration of study drug will be used for baseline.

6) Baseline **height and weight** are defined as the measurements taken at the run-in Visit 101. Missing baseline will not be imputed.

7) Baseline **ECG** is defined as ECG measured 35 minutes prior to the first dose of study drug on Day 1. Checks will be performed to ensure the ECG was indeed assessed prior to the first

dose of study drug. If it is missing (or not confirmed to be pre-dose), then the last assessment taken at the run-in Visit 101 or at an unscheduled visit before the first administration of study drug will be used. Otherwise, the ECG baseline will be set to missing without imputation.

